Background and Rationale	
Sporting activity is characterized by factors of the type, duration and intensity of exertion. Depending on the extent of these factors and the associated recovery time, damage to the muscles, inflammation and fatigue in the nervous system occur. Energy substrate degradation and local swelling also occur. Therefore, rapid regeneration after intensive sports has become all the more important. According to the meta-analysis by Bleakley et al. 2012, cold is considered to be one of the most effective recovery methods after sporting activity to delay delayed onset muscle soreness (DOMS). The DOMS are microscopic tears in muscle tissue called exercise-induced muscle damage, which can lead to delayed onset muscle soreness. DOMS usually peak between 24 and 48 hours – sometimes up to 72 hours – after exercise and are characterized by muscle shortening, increased passive stiffness, swelling, decrease in strength and power, localized muscle soreness, and altered proprioception.
 
The physiological background of cryotherapy is based on the removal of body heat by reducing tissue temperature. This is reflected in a reduced perception of muscle pain, so that the body feels more "awake" after training and causes less fatigue. In addition, due to the cold, the body lowers the heart rate and cardiac output, inducing vasoconstriction. The results are smaller vessel diameters, a reduced incidence of oedema and an improved oxygen supply to the cells. In order to maintain the body's core temperature, the central metabolism also increases, which promotes the transport of waste products. All these effects, in composition, could reduce the inflammation caused by exercise by reducing the death or damage of hypoxic cells and minimizing damage to secondary tissues by reducing the infiltration of leukocytes and monocytes. (Bleakley et al. 2012, Hohenauer E et al. 2015, Hubbard et al. 2004, Ostrowski et al 2018). Postoperative cryotherapy utilizing ice packs, cooling, or continuous cryotherapy devices reduced visual analogue scale pain scores and analgesic consumption in approximately half of the prior art research studies comparing these outcomes to the control group (no cryotherapy) (11 [44%] out of 25 studies on pain and 11 [48%] out of 23 studies on opioids). However, an effect in increasing range of motion (3 [19 %] out of 16) or reducing swelling (2 [22 %] out of 9) was reported less frequently. (Kunkle et al. 2021). The study induced here is intended to provide new data, especially in the reduction of swelling and inflammation values, and to confirm the reduction of pain by cold application of the Axanova Cold Hot Pearls Maxi Pack.


Risk / Benefit Assessment	In this examination, the risk can be classified as minimal. The product is applied as recommended by the manufacturer. The muscle soreness protocol is a protocol that has already been described in the scientific literature.
Objective(s)	The aim of this study is to investigate how local, repeated cold applications affect the recovery phase according to a muscle soreness protocol. Recovery is assessed at 24-hour intervals (up to 72 hours according to the muscle soreness protocol).
Endpoint(s)	
Primary endpoints:
 
 • Sore muscles (VAS 0 – 10 cm) • Inflammation levels (blood sinking velocity, C-reactive protein, creatine kinase) • Muscle swelling (in cm using ultrasound) • Maximum Voluntary Isometric Thigh Contraction (in kg) 
Secondary endpoints
 
 • Surface temperature of the skin (in °C) • Thermal Perception
Investigation Design	Randomized, controlled trial
Statistical Considerations	Repeated measure ANOVA, n=45 subjects
Inclusion- / Exclusion Criteria	
Inclusion Criteria
 
 • Young, healthy adults between the ages of 18 and 30 • No surgical interventions on the musculoskeletal system in the trunk area and lower extremities 
Exclusion criteria
 
 • Current pain conditions: Subjects with acute pain conditions. • Current inflammatory conditions: Presence of inflammation or known inflammatory diseases. • Medication intake (excl. anticonception drugs): Subjects taking medication, with the exception of anticonception drugs. • Pregnant subjects: Women who are pregnant or breastfeeding. • Competitive athletes: Test subjects who practice competitive sports. • Children/adolescents: Subjects under 18 years of age or over 30 years of age. • Non-intact skin conditions (e.g. psoriasis): Skin conditions, such as psoriasis or other non-intact skin conditions. • Known circulatory disorders: Presence of known circulatory disorders. • Cold allergy (Raynaud's syndrome): Allergy to cold or the presence of Raynaud's syndrome. • Previous operations on the upper body or legs: Operations in the areas of the body examined. • Disturbed perception in the thigh: Disturbances in the sensation of temperature or touch in the thigh area. • Diagnosed diseases: Presence of diagnosed diseases that could affect participation in the examination. • Smoking: When the subject smokes.
Number of Participants with Rationale	The study is planned with 3 study arms. The average initial VAS score after pain induction varies depending on the examination and is an approximation of an initial value of 4.73 ± 2.39 . A reduction in the VAS score after cold application was assumed to be an average of 47%. After taking into account the dropout rate of 10% and splitting into 3 randomized groups, a patient count of 15 subjects per study arm is considered statistically appropriate. The results were determined using the PASS 2023 version 23.0.1 software.
Intervention	The product "Cold Hot Pearls Maxi Pack" of the company Axanova AG is used for testing. This product has a gel bead filling that can be used for cold and heat applications. According to the manufacturer, the cold compresses must be stored in a freezer for at least 1 hour before they can be used. The cold pack can then be placed on the affected area on the fleece side, but for a maximum of 20 minutes in the same place.

	
In our study, there are 2 cooling groups:
 
The first group starts cooling immediately after the muscle soreness protocol.
 
The second group starts cooling 24 hours after the muscle soreness protocol.

Control Intervention	
The control group will not receive an intervention according to the muscle soreness protocol.

Investigation procedures	
Subject recruitment
 
The test subjects are recruited at the University of Physiotherapy THIM in Landquart and the University of Applied Sciences and Arts Southern Switzerland in Landquart.
 
The subject information and the declaration of consent are given to the test subjects. In the subject information there is a checklist that the test persons must fill out in order to check the inclusion and exclusion criteria.
 
If the subjects agree with the information, have completed the checklist and signed the consent, they will be summoned to make an appointment for the measurement.
 
Investigation Protocol
 
As soon as the signed consent of the test person has been received and an appointment has been made, the following procedure is followed. The anthropometric data of the subjects will be collected and group randomization will be carried out. Afterwards, the baseline measurements are carried out and the measurement of the skin temperature is started. Then the muscle soreness protocol (6 x 12 to 15 one-legged knee extensor protocol with a 2-minute break between sets) is completed. Cooling group A then receives the first 20-minute cooling of the thigh group.
 
Cooling group B and the control group leave the laboratory 20 minutes after the muscle soreness protocol. The measurement of skin temperature is stopped within all groups 20 minutes after the muscle soreness protocol.
 
Cooling group B begins cooling the thigh muscles 24 hours after the muscle soreness protocol. Both cooling groups perform cooling of the thigh muscles 3 x / day for the duration of the data collection (up to 72 hours according to the muscle soreness protocol).
 
At intervals of 24, 48 and 72 hours, the primary endpoints of the study are collected again. These include: muscle soreness, inflammation levels, muscle swelling, maximum voluntary isometric contraction of the thigh muscles.
 
Measurement of sore muscles
 
The level of ventrally felt muscle soreness symptoms is measured using a VAS scale (0 – 10 cm). The test subjects rate the perceived muscle soreness in both ventral thighs in a 90° knee flexion position. The measurement takes place during the baseline measurement and, 24 hours, 48 hours and 72 hours after the intervention.
 
Inflammation levels
 
The inflammation values (blood sedimentation rate, C-reactive protein, creatine kinase) are determined by venous blood sampling. The measurement takes place during the baseline measurement and, 24 hours, 48 hours and 72 hours after the intervention.
 
Muscle swelling
 
The measurement of muscle swelling of the quadriceps femoris muscle is carried out by ultrasound measurement. The measurement is carried out in a resting position and a cross-section of the muscle is recorded. The measurement takes place during the baseline measurement and, 24 hours, 48 hours and 72 hours after the intervention.
 
Measurement of maximum voluntary isometric thigh muscle contraction (MVIC)
 
MVIC is performed on an ergometer chair for biomechanical measurements and is given in kg. The measurement takes place during the baseline measurement and, 24 hours, 48 hours and 72 hours after the intervention.
 
Surface temperature
 
The surface temperature is measured using the iButton system. These sensors are glued to the skin for the duration of the measurement. The button sensors store the current temperature information and can then be read out via a computer. These measurements are started during the baseline survey, for the duration of the muscle soreness protocol, and up to 20 minutes after the muscle soreness protocol.
 
Detection of thermal perception
 
The thermal perception of the participants is recorded immediately after exposure to cold using the standardized Thermal Perception Scale (-4 to +4). This scale ranges from -4 ("extremely cold") to +4 ("extremely warm"), with 0 being considered neutral. The evaluation is carried out


	as a subjective self-assessment in order to document the individual temperature perception. Participants will be informed about the scale in advance. Since this is a purely subjective assessment, there is no risk for the participants.
Investigation Duration and Schedule	Planned start of measurements: 01/2025 Planned end of measurements: 07/2025
Investigator(s)	[name] [name] [name] Contact / Director of Studies [name] University of Applied Sciences Southern Switzerland Physiotherapy Graubünden [name] [contact] [contact]
Investigation Center(s)	University of Applied Sciences Southern Switzerland Physiotherapy Graubünden Rehabilitation Research Laboratory RESlab SUPSI Landquart, [name]
Data privacy	The data are only accessible to the head of the study ([name]) and persons of the KEK (in case of any quality controls on site). The data is coded numerically (001, 002, 003, etc.). Only the study leader can solve the code. All data is stored in the laboratory of the University of Applied Sciences and Arts Southern Switzerland in Landquart.
Ethical consideration	Athletes could benefit from these results as they receive information on how they could increase their athletic performance or recovery by applying cold after exercise. The methodological approach is based on the current scientific literature. The risk can be considered minimal because the product is used as prescribed.
Compliance statement	This investigation will be conducted in full compliance with the CIP, the current version of the Declaration of Helsinki, ISO 14155 [2024], ICH-GCP (as far as applicable) as well as all national legal and regulatory requirements.

ABBREVIATIONS

AE	Adverse Event
AIP	Azure Information Protection
ASR	Annual Safety Report
BASEC	Business Administration System for Ethical Committees
ClinO	Ordinance on Clinical Trials in Human Research (in German: KlinV, in French: OClin, in Italian: OSRUM)
CRF	Case Report Form
CTCAE	Common Terminology Criteria for Adverse Events
CATHEDRAL	Delayed Onset Muscle Soreness
eCRF	electronic Case Report Form
FADP	Federal Act on Data Protection (in German: DSG, in French: LPD, in Italian: LPD)
FOPH	Federal Office of Public Health
GCP	Good Clinical Practice
HRA	Human Research Act (in German: HFG, in French: LRH, in Italian: LRUM)
I	International Conference on Harmonisation
ISO	International Organisation for Standardisation
MDR	Medical Device Regulation
MVIC	Maximum Voluntary Isometric Contraction
SAE	Serious Adverse Event
SDV	Source Data Verification
SSL	Secure Sockets Layer
SUE	Serious Unexpected Events
TLS	Transport Layer Security
UAE	Unanticipated Adverse Event

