a TANITA-TBF 611 scale (Tokyo, Japan). The estimate of the percentage of lower body fat was chosen because the cold pack was applied to the thigh, which mainly affects the lower extremities. Recovery parameters (see Exact Measurement Method and Primary and Secondary Endpoints) are assessed in the same order for each measurement: (1) Inflammation Scores, (2) Muscle Swelling, (3) Soreness, (4) Maximum Voluntary Isosomic Muscle Contraction. The measurement method and the equipment used for each specific result are described in Chapter 3.2.

Randomization

The randomization of the subjects will take place on the day of the baseline measurement by drawing a lot. It is ensured that the same number of tickets are available for each intervention group (5 tickets per group) and test subjects. If the number of subjects in a group exceeds one third of the total number of subjects, the lots of this group will be removed. In order to ensure the equality of the groups in terms of covariates and gender, the composition of the groups is monitored. As soon as half of a group consists of male or female subjects, the tickets for this group are removed for future subjects of the same sex.

The tickets are made of folded paper with the numbers 1, 2 or 3 on them and are placed together in a container. The drawing of the lots is carried out by the test persons themselves. After the draw, the subjects hand over the unread ticket to the study director, who assigns them to a group.

Blinding

Since cold applications are tested in this study, blinding is not possible.

Sore muscle protocol

To induce muscle soreness, a one-legged knee extensor protocol is used, which has already been used (Ruas et al., 2022). Participants will be instructed to straighten and bend their knee for 6 sets for 12 – 15 reps, with 2 minutes rest between sets. During the 2-minute break, the participants are allowed to sit on the chair. The execution of the knee extensor protocol is visually observed by an examiner. Verbal corrections of the execution can be given by the examiner. However, no verbal encouragement is given. All training sessions are carried out in the morning. If a participant is unable to perform all the repetitions of a set due to extreme fatigue or maximum effort, the set can be stopped and a new set can be started after the rest period. However, at least 12 repetitions per set must be performed. Otherwise, this will be considered an abandonment.

Intervention

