The subjects in group A (immediate cooling) receive the first cooling on the two thighs immediately after the end of the muscle soreness protocol. This cooling is carried out in the supine position. After this application, you can leave the laboratory and the measurement of the skin temperature is stopped.

Group B (delayed cooling) and group C (control group) do not receive any cooling (group B) or any intervention (group C) immediately after the muscle soreness protocol. However, you will also need to spend 20 minutes lying on your back in the lab before the skin temperature measurement is completed.

Follow-up measurements

Follow-up measurements will be taken for each measurement in the same order as for the baseline measurement ((1) Inflammatory markers, (2) Muscle swelling, (3) Soreness of muscles, (4) Maximum voluntary isometric contraction). The follow-up measurements take place 24, 48, and 72 hours after the muscle soreness protocol in the laboratory in Landquart.

The measurement method and the equipment used for each specific result are described in Chapter 3.2.

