δ_i	The difference between the i th treatment agent and the control agent ($\mu_i - \mu_c$) for which the test strength is calculated.
σ	The standard deviation of the responses within each group.
Alpha	The probability of rejecting the null hypothesis that the control mean is equal to the treatment mean described in this row.

Summary statements

A parallel 3-group design (with a control group and 2 treatment groups) is used to test whether the mean for each treatment group is different from the mean of the control group ($H_0: \delta = 0$ versus $H_1: \delta \neq 0, \delta = \mu_i - \mu_c$). The hypotheses are evaluated using two two-sided, two-sample methods. Bonferroni-adjusted t-tests with the same variance and an overall (experimental) Type I error rate (α) of 0.05. The common standard deviation for all groups is assumed to be 2.1. The mean value of the control group is assumed to be 4.72. The treatment means 2.21 and 1.87 with at least 80% test strength to be detected in each case. For the test, the (same) group sample size needed for each of the three groups (control and treatments) is 13 (39 subjects in total). The group sample sizes were calculated using PASS 2023, version 23.0.1.

Sample size taking into account the dropout rate

Group	Dropouts Abandonment Rate	Number of cases/group	Number of cases with drop-out rate	Number of abandoned participants
1 - 3	10%	13	15	2
Total	n/a	39	45	6

Taking into account the drop-out rate

Taking into account a dropout rate of 10%, the group sizes in each study arm should be 15 subjects.

Statistical approach to examine the primary endpoints

The statistical analysis is performed using IBM SPSS Statistics (version 27, IBM Corp., Armonk, NY, USA) and the significance level is set to $p < 0.05$.

In order to be able to determine the differences between groups, a repeated ANOVA analysis is carried out with a factor of 1: time (baseline, 24 hours, 48 hours, 72 hours) and a factor of 2:

intervention (group A, group B, group C) for the recovery parameters (inflammation values, muscle swelling, muscle soreness data, maximum voluntary isometric muscle contraction).

The examination is discontinued if the participants are intolerant to the local cold application. Participants in the IC and DC groups are instructed to cancel a cooling session and contact their contact immediately if they experience symptoms such as severe pain/discomfort as a result of the cooling.

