4.2. Handling of missing data and drop-outs

Missing data, missed training sessions or abandonments are noted in the CRF. Data from patients who discontinue the examination is collected and stored. Drop-outs are not replaced by the recruitment of new participants. If consent is withdrawn, the data already collected will be included in the analysis for scientific and safety reasons. These are only anonymised after the analysis (Art. 32 ClinO-MD).

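### The lot is drawn before the soreness exercise and nothing withholds the group until the exercise ends, although all three arms are handled alike until then

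*Combined protocol and SAP*

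**What the plan says.** The synopsis (Investigation Protocol) gives the day-1 sequence: "The anthropometric data of the subjects will be collected and group randomization will be carried out. Afterwards, the baseline measurements are carried out". The exercise comes next, and then the first cooling, in group A only.

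Section 3.3, Randomization, fixes only the day: "The randomization of the subjects will take place on the day of the baseline measurement by drawing a lot". The headings of section 3.3 run baseline, randomisation, blinding, exercise, intervention. They therefore agree with the synopsis that the draw precedes the exercise, but they do not confirm that it precedes the baseline measurements.

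On who learns the group: "After the draw, the subjects hand over the unread ticket to the study director, who assigns them to a group". On blinding: "Since cold applications are tested in this study, blinding is not possible".

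The exercise is 6 sets of 12 to 15 repetitions with 2 minutes of rest. An examiner watches, may correct execution and gives no encouragement. No load is stated. The completion rule is: "However, at least 12 repetitions per set must be performed. Otherwise, this will be considered an abandonment". After the exercise group A is cooled lying down, and for groups B and C: "However, you will also need to spend 20 minutes lying on your back in the lab before the skin temperature measurement is completed".

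For the analysis, section 4.1 says "a repeated ANOVA analysis is carried out with a factor of 1: time (baseline, 24 hours, 48 hours, 72 hours", with intervention group as the only other factor. Section 4.2 has abandonments noted in the CRF and adds: "Drop-outs are not replaced by the recruitment of new participants".

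**The concern.** The exercise creates the soreness whose recovery is the outcome, and the amount of it depends partly on effort. If the subject or the observing examiner already knows the group, effort, corrections and abandonment could differ between arms before any treatment has been given. On the synopsis order the same holds for baseline MVIC, an effort-dependent primary endpoint that supplies the first level of the time factor.

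An ANOVA with time and intervention only would attribute such a difference to the intervention. A subject who abandons during the exercise would be a post-randomisation loss without having been treated, and would not be replaced.

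The reason given for having no blinding is that cold is being tested. That reason covers the period from the first cooling onward. It does not cover baseline or the exercise, when no arm is cooled.

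**Working it through.** **Order of events, side by side**

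| Step on day 1 | Synopsis | Section 3.3 | Same in all arms? |
|---|---|---|---|
| Anthropometry | 1st | under Baseline measurements | yes |
| Draw of lot | 2nd | day of baseline; heading after baseline, before exercise | yes |
| Baseline measurements | 3rd | heading before the draw | yes |
| Exercise, 6 sets | 4th | after the draw | yes |
| 20 minutes after exercise | 5th | group A cooled; B and C supine without cooling | **no, first difference** |

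So the group is not needed for any procedure until the sixth set is finished. The nearest safeguard is the unread ticket. It stops the subject reading the lot at the draw, but the study director then assigns the group, and no time is given at which the subject or examiner learns it.

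**Can a difference in work be seen afterwards?** Section 4.2 records abandonments. The data listed in section 7.2 include neither repetitions completed nor load.

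**The plan's planning figures.** Section 4.1 assumes means of 4.72 (control) and 2.21 (group A) and an SD of 2.1. The difference is 4.72 − 2.21 = 2.51. A two-sided equal-variance t-test at alpha 0.05 with 13 per arm gives power 0.83233, as the plan states.

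**Illustration of size.** The documents give no size, so two assumptions are shown. The permitted total is 6 × 12 = 72 to 6 × 15 = 90 repetitions, with a midpoint of 13.5 per set. Let g be the mean gap between two arms in repetitions per set, split evenly around 13.5, so that one arm is at 13.5 + g/2 and the other at 13.5 − g/2.

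(a) Soreness proportional to repetitions in both arms. If control does more:
difference = 4.72 × (1 + g/27) − 2.21 × (1 − g/27) = 2.51 + 6.93 × g/27.
If group A does more, the sign of the shift reverses.

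(b) Soreness proportional to repetitions, but cooling subtracts a fixed 2.51 cm:
shift = 4.72 × g/13.5.

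| g per set | (a) shift, cm | (a) share of 2.51 | (a) apparent difference | (b) shift, cm | (b) share of 2.51 | (b) apparent difference |
|---|---|---|---|---|---|---|
| 0.5 | 0.13 | 5% | 2.38 or 2.64 | 0.17 | 7% | 2.34 or 2.68 |
| 1 | 0.26 | 10% | 2.25 or 2.77 | 0.35 | 14% | 2.16 or 2.86 |
| 2 | 0.51 | 20% | 2.00 or 3.02 | 0.70 | 28% | 1.81 or 3.21 |

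A gap of 2 uses 2/3 of the permitted range of 15 − 12 = 3 and is an extreme case.

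**If there were no true effect.** For the same t-test with 13 per arm and SD 2.1, assumed shifts of 0.25, 0.5 and 1.0 cm would raise the nominal 5% rejection rate to about 6.0%, 9.0% and 21.4%. This is the test used for sample size, not the planned ANOVA.

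**The case against.** The strongest case on the other side has four parts.

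- **Early disclosure is not documented.** The ticket goes unread to the study director, and the examiner who watches the exercise is not said to be that person. The text is compatible with neither subject nor examiner knowing. This stands. A reader might infer that subjects are told their group before they exercise; the documents do not say so. What is missing is a safeguard.
- **The exercise is constrained.** The repetition range is narrow, rest is fixed, execution is observed and encouragement is barred. This limits the risk but leaves effort, load and corrections open.
- **Imbalance is partly visible.** A reader might conclude that no difference between groups before treatment could be checked. That goes too far: abandonments are noted in the CRF, and the CRF itself is not among the documents. Only repetitions and load are absent from the list in section 7.2.
- **Follow-up is open-label anyway,** with self-rated soreness and effort-dependent MVIC. This is true, and the change proposed here does not alter it. But exposure that cannot be avoided later is no reason to accept exposure that can be avoided earlier.

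On size, a reader might take 0.70 cm (28%) as the expected distortion. It combines an extreme gap with a fixed cooling effect, whereas section 4.1 describes the assumed effect as a percentage reduction, which is closer to assumption (a).

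**Conclusion.** The concern holds as an avoidable risk of bias that comes from the order of day 1. The draw precedes the exercise in both places that describe it. Only the synopsis also puts it before the baseline measurements, so the point about baseline MVIC depends on that order. No text keeps the group from the subject or examiner until the sixth set is done, and nothing before then requires it to be known.

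Neither size nor direction can be taken from the documents: the effect could imitate a benefit of cooling or hide one. Under assumption (a), realistic gaps of 0.5 to 1 repetition per set move the planned difference by 5% to 10%, and the extreme case by 20%. These figures rest on proportionality between soreness and repetitions, which is assumed. The point does not invalidate the trial, but the change is cheap and should be made.

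**What to change.** 1. In the synopsis and in section 3.3 (Randomization), place the draw after the baseline measurements and the sixth set, immediately before the 20-minute supine period.
2. State in section 3.3 that the group has not been drawn during baseline and exercise, and that the study director does not disclose which tickets remain. Tickets are removed when a group is full or half of it is of one sex, so late allocations can become predictable.
3. State in section 4.2 that subjects who abandon under the existing repetition rule have not been randomised, so the no-replacement rule does not apply to them, and report their number.
4. Add repetitions completed per set and the load used to the data recorded under section 7.2.

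Drawing early and keeping the ticket closed until the exercise ends is not an adequate substitute. The ticket-removal rule needs earlier allocations to be known before the next subject draws, and a subject who abandons would already hold a lot.

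Cost: one step moves within the same visit, two CRF fields are added, and a few more volunteers may be needed to reach 45 randomised. Having packs ready at every day-1 visit is not a new cost. The packs need 1 hour of freezing (section 2.4) and the visit is scheduled for 60 minutes (section 3.3), so they must already be in the freezer before the group is known.
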